Purpose:	To evaluate the effect of the NxThera BPH Rezūm System on prostate tissue in subjects suffering from LUTS symptoms secondary to benign prostatic hyperplasia (BPH).
Study Design:	
This study is a single center study. It will be carried out in two phases on subjects with benign prostatic hyperplasia.
 
Phase 1: Acute study - In-vivo treatment of the prostate in subjects scheduled to have a surgical TURP or full excision of the prostate. Prostate tissue will be excised after treatment as part of the planned surgery. There is no follow up.
 
Phase 2: Optimization study - Subjects with BPH symptoms will be treated with the Rezūm device with a range of thermal energies (as measured by calorie output) to optimize the setting for maximum lesion size with minimal intra and post procedure discomfort. The lesion size and ablated tissue resorption rate will be followed post-procedure via MRIs.

Enrollment:	
Phase 1: Up to 20 BPH subjects scheduled for surgical removal of the BPH tissue
 
Phase 2: Up to 15 BPH subjects suffering from BPH symptoms.

Target Subject Population:	
 • Male subjects \geq 45 years of age who have symptomatic / obstructive symptoms secondary to BPH requiring surgical intervention.
Follow-up:	
Phase 1 – Acute, no follow up
 
Phase 2 – 1 day, 1 week, 1 month, 3 months, 6 months, 12 months, and annually thereafter up to 5 years.

Phase 1 Endpoint	Lesion size and characteristics as evaluated using Tetrazolium Chloride (TTC) stain and histopathologic evaluation of representative samples.
Phase 2 Endpoints	
Lesion characterization via MRI
 
Intra and post procedure discomfort
 
Catheterization post procedure
 
The change (improvement) from baseline in International Prostate Symptom Scores (IPSS) at day 1, week 1, month 1, months 3,6 and 12, and annually thereafter up to 5 years

CONFIDENTIAL: Contains Proprietary Information

Study and Data Management:	Libra Medical, Inc. [name] [contact] [contact] Email: [contact]
Study Monitors:	Libra Medical, Inc. [name] [contact] [contact] Email: [contact]
Sponsor:	NxThera Inc [name] [contact]

TABLE OF CONTENTS

1	BACKGROUND.....	8
2	SUMMARY DEVICE DESCRIPTION.....	8
3	SUMMARY OF PROCEDURE	9
4	PHASE I ACUTE STUDY DESIGN.....	12
5	PHASE 2: OPTIMIZATION STUDY	13
6	STUDY PROCEDURES	15

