4.1 PHASE 1: ACUTE STUDY

The subjects will undergo a Rezūm procedure per the IFU with the Delivery Device inserted transurethraly in order to deliver the therapy directly into the prostate. The treatment setting used will be based on the results obtained from treating extirpated prostate tissue from Rezūm Ex study. After vapor ablation, the planned prostatectomy/adenectomy surgical procedure will continue until completion. Information regarding usability, treatment settings, and correlation to the lesion size will be collected from an examination of the extirpated tissue. The lesions from the extirpated prostate tissue will be necropsied and evaluated for lesion characteristics to gain additional information to optimize the vapor ablation treatment.

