4.1.1 Acute: Inclusion Criteria

- 1. Male subjects \geq 45 years of age who have symptomatic / obstructive symptoms secondary to BPH requiring invasive intervention.**
- 2. Scheduled to have prostatic tissue surgically removed.**

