4.2 TREATMENT MEDICATION

There are no treatment medication requirements for this portion of this study. Medication will be administered at the discretion of the Principal Investigator or his designee per the standard hospital procedure for adenectomy. .

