4.3 SAMPLE SIZE

Up to 20 BPH subjects scheduled for surgical removal of BPH tissue

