4.4 STUDY DURATION

There is no follow up for this acute study. Therefore, study duration is anticipated to be no more than 2 weeks.

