4.5 ENDPOINT

Lesion size from the vapor treatment, as measured by TTC stain in the extirpated tissue.

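### Does naming TURP only in the synopsis leave the Phase 1 lesion-size summary undefined?

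*Combined protocol and SAP*

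**What the plan says.** The synopsis gives the Phase 1 population as "In-vivo treatment of the prostate in subjects scheduled to have a surgical TURP or full excision of the prostate". It is the only place where TURP is mentioned. The second inclusion criterion in Section 4.1.1 names no operation: "Scheduled to have prostatic tissue surgically removed". Section 4.3 is equally general: "Up to 20 BPH subjects scheduled for surgical removal of BPH tissue". Section 14.1 says only that Phase 1 subjects are scheduled for surgery, and the exclusions in Section 4.1.2 do not bar a planned TURP.

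Two places use narrower words. Section 4.1 states: "After vapor ablation, the planned prostatectomy/adenectomy surgical procedure will continue until completion". Section 4.2 leaves medication to the investigator's discretion "per the standard hospital procedure for adenectomy".

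The endpoint in Section 4.5 is "Lesion size from the vapor treatment, as measured by TTC stain in the extirpated tissue". Section 14.8.8 gives the method: the specimen is laid out, sliced serially and stained, and treatment volume is estimated from the slices. Section 4.1 also plans to relate settings to lesion size: "Information regarding usability, treatment settings, and correlation to the lesion size will be collected from an examination of the extirpated tissue". Section 14.2 plans descriptive statistics as appropriate and requires every enrolled subject to be accounted for. It defines no evaluable set for Phase 1.

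**The concern.** The synopsis itself distinguishes TURP from full excision, so the protocol recognizes two kinds of specimen but describes one method of measurement. Serial slicing reads most naturally as a method for a specimen in one piece. If TURP tissue came out in fragments, or held only part of the ablated zone, the method would not fit it.

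A man could then receive the investigational ablation without contributing to the one endpoint in Section 4.5. Section 4.4 rules out a later measurement: "There is no follow up for this acute study". Pooling partial specimens would mix the effect of the treatment setting with the extent of the resection. Dropping them without a stated rule would mean choosing the denominator with the results in hand. Either would touch the lesion-size mean and the planned comparison of settings with lesion size.

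**Working it through.** The documents give no formula, variance or target for Phase 1, so the check is a comparison of sections.

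**1. Who may enter Phase 1?**

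| Place | Surgery named | Role of the text |
|---|---|---|
| Synopsis, Study Design | TURP or full excision | defines population |
| Synopsis, Enrollment | surgical removal of BPH tissue | defines population |
| 4.1.1, criterion 2 | any surgical removal of prostatic tissue | defines eligibility |
| 4.3 | surgical removal of BPH tissue | defines sample |
| 14.1 | surgery, not specified | defines recruitment |
| 4.1 | prostatectomy/adenectomy | narrative of the procedure |
| 4.2 | adenectomy | medication practice |

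The five entries that define the population are compatible with one another, and all can include TURP. The two narrower entries do not set eligibility, and they differ from each other. That points to loose terminology rather than a deliberate restriction. Prostatectomy is not defined and can be read broadly. The result is a mismatch of wording, not a contradiction about who is eligible.

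**2. Does the endpoint exclude TURP tissue?** Section 4.5 refers to tissue that has been removed, without requiring a whole gland. Section 14.8.8 speaks of the prostate, but Section 14.8.11 uses the removed tissue and the treated prostate as names for the same object. The prostate in Section 14.8.8 may therefore mean only what was taken out. The text does not show that TURP tissue falls outside the method, nor does it say how such tissue is to be measured.

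**3. How many values could be lost?** With a cap of 20 and a TURP share p, the number measurable is 20 × (1 − p) if TURP tissue yields nothing, and 20 if it always yields a value. Neither p nor the yield is in the documents. Across p from 0 to 1 the count runs from 20 to 0, so the documents do not narrow it at all.

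**4. What depends on that count?** Section 4.3 gives an upper limit with no precision or power behind it, so no stated requirement is missed at any count. Section 4.1 takes the Phase 1 setting from an earlier study on removed tissue. Section 5.2 says the acceptable power range for Phase 2 has already been determined from bench, animal and removed human tissue. No section contains a rule of the form: if mean Phase 1 lesion size is above or below some value, then act.

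**5. Could a missing value go unnoticed?** Section 6.1 counts a subject as officially enrolled only if treatment is attempted, so every treated subject is enrolled. Section 14.2 requires all enrolled subjects to be accounted for. A treated man with no lesion measurement would therefore have to appear in the subject accounting.

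**The case for a change.** The strongest reply is that the ambiguity is itself the reason for a rule. Two careful analysts could take the same data, one pooling partial specimens and the other leaving them out, and report different means and denominators. Section 4.1 says the lesion findings will inform optimization of the treatment, so the summary has some use even without a formal decision rule. The number of subjects is small, the treatment is investigational, and a sentence in Section 4.5 or 14.8.8 would cost almost nothing.

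Part of this stands. The silence is real: no section says whether TURP tissue is pooled, shown separately or left out. Accounting for a subject is also not the same as saying whether his value enters the mean.

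What does not stand is the step from silence to a wrong result. That step needs TURP cases to occur and their tissue to be unmeasurable or misleading, and the documents establish neither. The two obvious rules are no clear improvement. Narrowing eligibility to the surgery named in Section 4.1 could slow recruitment, would change nothing if no TURP cases are expected, and would leave Section 4.2 worded differently from Section 4.1. Nor would it secure complete specimens, since no section says adenectomy is full excision. Leaving all TURP tissue out of the summary would discard data on an unverified assumption about how the specimens look.

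**Conclusion.** No change to the plan is called for. The wording on Phase 1 surgery is uneven, and the handling of TURP specimens is unstated. This is a detail that analysts of a small descriptive phase fill sensibly: report lesion size for each specimen in which it can be measured, give the number measured and the type of surgery, and state why any value is missing. No hypothesis test, precision target or stated decision rule changes with the answer.

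The size of any effect on the lesion-size summary cannot be computed from the documents, and it is zero if no TURP subjects enroll. The conclusion rests on two assumptions: that Phase 1 stays descriptive, as Section 14.2 describes it, and that the accounting of all enrolled subjects is carried through to the report of lesion size. If the protocol is amended for another reason, using one set of surgical terms in the synopsis and in Sections 4.1, 4.1.1 and 4.2 would be a harmless tidying. Which operations should be allowed is a clinical matter and is not judged here.

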1 BACKGROUND

NxThera has completed more than 60 canine studies as part of its convective vapor ablation system product development program. Collectively, these studies are best classified as a series of investigational studies that were an integral part of the Company's efforts to develop and validate the safety of the system and the treatment of the prostate with vapor therapy, and to optimize the therapeutic delivery of vapor to effectively treat benign prostatic hyperplasia (BPH).

An earlier version of the Rezūm System has been tested in human subjects. This initial study included four acute subjects and 9 chronic subjects with up to 6 months follow-up and a subset of these chronic patients with 12 month follow-up data. This study repeats the same study but using the revised Rezūm System that is intended for commercial use.

2 SUMMARY DEVICE DESCRIPTION

The NxThera BPH Rezūm System consists of the following components:

- Power Generator**
- Delivery Device (which includes an insulated introducer sheath and vapor delivery needle)**
- Water delivery system**
- Saline flush tubing**

Figure 2-1: Rezūm System (not drawn to scale)

The NxThera BPH Rezūm System consists of a RF power Generator unit which controls the generation and temperature of the water vapor created at the Delivery Device and delivered to the prostate.

Within the Delivery Device is an insulated shaft with two lumens, one of which is used for a 4 mm cystoscopy optical lens. The other lumen contains the vapor delivery plastic needle. At

the distal end of the vapor needle, the vapor emitter holes are arranged circumferentially around the needle through which water vapor is delivered to the prostate when the needle is inserted within the prostate.

The Rezūm Generator system has been built in compliance with quality control system (IEC 60601-1) and both the hardware and software of the system have gone through verification and validation testing, including controlling the vapor delivery.

The procedure utilizes a transurethral approach under direct visualization using the optics from a standard rigid cystoscope which is inserted into the Delivery Device to allow the treating physician to visualize access to the prostate through the urethra, and to facilitate proper placement of the vapor needle into the prostate to deliver the vapor therapy. Using the bladder neck and veru montanum as the anatomical guides (e.g., the transition zone of the prostate), the tip of the Delivery Device is positioned against the wall of the urethra; the physician then releases the safety and deploys the vapor needle into the prostate.

Once the needle is fully deployed, the vapor treatment button is activated to deliver the water vapor for up to 10 seconds of treatment. This process is repeated as many times as needed for each lobe of the prostate, with the first treatments delivered near the bladder neck. The standard treatment algorithm is to leave approximately 1 cm between each treatment injection, and a typical sized prostate with BPH will need three 10-second treatments in each lateral lobe. The median lobe, if present, may be treated with one or two treatments.

Potential benefits of this treatment, in contrast with other transurethral ablation treatments, are:

- No electromagnetic energy is delivered within the body.
- Each treatment is up to 10 seconds; each lateral prostate lobe may receive 2-4 treatments or one treatment per 1 cm length of urethra within the prostate
- Median lobes of all sizes can be treated.
- Treatments may be done with no or minimal local anesthesia.
- There may be less bleeding, post procedure, than with other treatments.
- Symptom relief is expected within days of treatment.

3 SUMMARY OF PROCEDURE

1. Insert the 4 mm optical lens of a rigid endoscope into the Delivery Device;
2. Evaluate the Rezūm system readiness by doing a test treatment in air;
3. Lubricate the shaft of the Delivery Device with Lidocaine gel or equivalent;
4. Insert the shaft of the Delivery Device into the urethra until the tip is in the bladder using the endoscopy view to guide the Delivery Device;
5. Withdraw the tip of the Delivery Device to just below the bladder neck;
6. Press the tip of the shaft against the urethra, and press the flush button as necessary to visualize placement;

7. **Depress the trigger to deploy the vapor needle into the prostate tissue. Ensure that the indicator mark on the vapor needle is fully inserted into the prostate**
8. **Pull the vapor trigger to deliver the vapor therapy. The power will be automatically shut off after 10 seconds (or earlier if the vapor trigger is released prior to 10 seconds).**
9. **Retract the vapor needle;**
10. **Reposition the tip of the Delivery Device 1 cm from the first treatment position;**
11. **Repeat the process with the contralateral lobe and the median lobe (if present). See Figure 3-3 as an illustration of the final results**

[figure not shown]

Figure 3-1: Vapor Delivered Through Vapor Needle

Figure 3-2: Prostatic Urethra After 3 Treatments on the Left Lobe

[figure not shown]

Figure 3-3: Schematic of Ablation Zone After Treatment

4 PHASE I ACUTE STUDY DESIGN

This study will be conducted in two phases. The phases will run consecutively. Both phases are part of a single arm, single center study.

4.1 PHASE 1: ACUTE STUDY

The subjects will undergo a Rezūm procedure per the IFU with the Delivery Device inserted transurethraly in order to deliver the therapy directly into the prostate. The treatment setting used will be based on the results obtained from treating extirpated prostate tissue from Rezūm Ex study. After vapor ablation, the planned prostatectomy/adenectomy surgical procedure will continue until completion. Information regarding usability, treatment settings, and correlation to the lesion size will be collected from an examination of the extirpated tissue. The lesions from the extirpated prostate tissue will be necropsied and evaluated for lesion characteristics to gain additional information to optimize the vapor ablation treatment.

4.1.1 Acute: Inclusion Criteria

- 1. Male subjects \geq 45 years of age who have symptomatic / obstructive symptoms secondary to BPH requiring invasive intervention.**
- 2. Scheduled to have prostatic tissue surgically removed.**

4.1.2 Acute: Exclusion Criteria

- 1. Presence of a penile implant;**
- 2. Any prior minimally invasive intervention (e.g. TUNA, Microwave) or surgical intervention to treat the symptoms of BPH;**
- 3. Confirmed or suspected malignancy of prostate;**
- 4. Previous pelvic irradiation or radical pelvic surgery;**
- 5. Urethral strictures, bladder neck contracture or muscle spasms; or,**
- 6. Biopsy of prostate within 30 days prior to the date of this procedure.**
- 7. Unable or unwilling to sign the Informed Consent Form**

4.2 TREATMENT MEDICATION

There are no treatment medication requirements for this portion of this study. Medication will be administered at the discretion of the Principal Investigator or his designee per the standard hospital procedure for adenectomy. .

4.3 SAMPLE SIZE

Up to 20 BPH subjects scheduled for surgical removal of BPH tissue

4.4 STUDY DURATION

There is no follow up for this acute study. Therefore, study duration is anticipated to be no more than 2 weeks.

4.5 ENDPOINT

Lesion size from the vapor treatment, as measured by TTC stain in the extirpated tissue.

5 PHASE 2: OPTIMIZATION STUDY

5.1 STUDY OBJECTIVE

The objectives of the Phase 2 study are:

Optimize the effectiveness of the BPH Rezūm System and assess the effect of treatments with different caloric values, including an assessment of subject comfort during the procedure and post-procedure

Further document the safety and post-operative effects of the Rezūm System in the treatment of obstructive BPH.

5.2 STUDY DESIGN

In this Phase 2 study, up to 15 subjects with LUTS secondary to BPH requiring surgical treatment will be treated with the Rezūm System. Treatment is ≤ 10 seconds per treatment. The power and water flow rate settings may be adjusted slightly to minimize pain and swelling to the subjects while maximizing the treatment area (e.g., lesion size). The power setting will be between 175W and 250W with a concomitant adjustment to the water flow rate of 2.7 ml/min to 5.0 ml/min. The actual power output will be recorded. For all the treatment settings, adverse and subject responses will be collected. The range of acceptable power setting have been determined in bench-top, animal studies, testing on extirpated human prostate to create lesions of a size that is adequate to treat the BPH tissue. The unknown factor that will be evaluated in this Phase 2 study is the acute response(s) to the different treatments in terms of procedural and post procedural discomfort. If the subjects are able to tolerate the higher caloric treatments, those treatments will be used in subsequent subjects. If the subjects are not able to tolerate a particular caloric treatment, the lower caloric treatment will be used in subsequent subjects.

The standard Rezūm treatment following the IFU will be followed. Information regarding the vapor needle configuration, treatment settings, treatment medications, pain or discomfort during treatment, post-treatment catheterization requirements, and the type and severity of any short term irritative or urinary obstructive symptoms will be collected. Information regarding the subjects' symptomatic response and uroflowmetry characteristics will be collected at baseline and in follow-up evaluations conducted with each subject. Any adverse events will be evaluated at each visit. Lesion characteristics and treated tissue resorption rate will be measured by gadolinium enhanced MRI imaging techniques performed post-procedure at specified intervals.

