5.3 OPTIMIZATION ENDPOINTS

5.3.1 Endpoint 1: Intra-procedure Pain

Procedural pain will be assessed using the Wong Baker scale. Subjects will be asked to rate the level of pain and discomfort during the treatment.

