5.3.2 Endpoint 2: Post-Procedure Catheterization

All subjects will be kept at the clinic for observation for 24 hours post-procedure. Post procedure catheterization will only be allowed if the Principal Investigator determines that

the subject has symptoms of retention (defined as failure to void within 8 hours post procedure) or requires catheterization for other safety reasons.

5.3.3 Endpoint 3: Lesion size, as measured by MRI at Week 1 post-procedure.

5.3.4 Endpoint 4: Change in IPSS score from baseline at various points post-procedure.

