7 ADVERSE EVENTS

7.1 DEFINITION OF ADVERSE EVENT(S)

For the purpose of this protocol, an “adverse event” (AE) will be defined as any adverse medical condition change (i.e., *de novo* or increased severity in a preexisting condition) from the subject’s baseline condition that occurs during the course of the clinical study, after starting study procedure, whether considered procedure-related or not. Therefore, conditions existing at the time of enrollment will not be reported as an AE unless the event increased in clinically significant severity during the course of the study. Events which resolve and then recur should be reported as separate AEs. Events that are a continuation of an unresolved AE should not be reported as a new AE but a continuation of the previously reported AE.

The reason for catheterization will not be considered an AE if catheterization occurs and ends within 72 hours after the procedure because this is generally considered standard of care to allow the tissue to heal.

The reason for catheterization will be considered an adverse event if the following applies:

- a. If catheterization occurs within a 72-hour window after the procedure and the duration of catheterization extends beyond that 72-hour window
- b. If catheterization occurs outside of a 72-hour window after the procedure
- c. If catheterization recurs after the same symptom is resolved

Lower Urinary Tract Symptoms (LUTS) will not be considered an adverse event if LUTS occurs and ends within a 3-day window (72 hours) after the procedure.

Lower Urinary Tract Symptoms (LUTS) will be considered an adverse event if the following applies:

- a. If LUTS occurs within a 3-day window (72 hours) after the procedure and the duration of LUTS extends beyond that 3-day window (72 hours)
- b. If LUTS occurs outside of a 3-day window (72 hours) after the procedure
- c. If LUTS recurs after the same symptom is resolved

Normally expected symptoms caused by the treatment will not be considered AEs for this study. For example, normal pain or minor bruising at the surgical site due to the healing of the site will not be considered an AE. “Treatment” includes all procedures and treatments administered according this protocol.

An AE may be volunteered spontaneously by the subject or discovered as a result of questioning or by physical examination by the investigator.

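### Phase 2 reuses or raises a caloric setting once it is tolerated, with no required pause after a related SAE and no minimum observation before an increase

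*Combined protocol and SAP*

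**What the plan says.** Section 5.1 aims to optimize effectiveness, to "assess the effect of treatments with different caloric values", and to document safety further. Section 5.2 treats up to 15 subjects at 175 to 250 W, with water flow moved alongside between 2.7 and 5.0 ml/min. It says that the power and flow "settings may be adjusted slightly to minimize pain and swelling to the subjects while maximizing the treatment area", and that the unknown to be evaluated "is the acute response(s) to the different treatments in terms of procedural and post procedural discomfort". The rule for later subjects is: "If the subjects are able to tolerate the higher caloric treatments, those treatments will be used in subsequent subjects". The next sentence sends later subjects to the lower setting if a setting is not tolerated.

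Safety data are gathered. Section 5.2 adds: "For all the treatment settings, adverse and subject responses will be collected". Catheterization is Endpoint 2 in 5.3, and 5.3.2 states: "All subjects will be kept at the clinic for observation for 24 hours post-procedure".

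After an SAE, 7.6 and Table 13-1 give the Principal Investigator up to 10 working days to tell the sponsor (48 hours for a death, in Table 13-1). Under 7.6 the sponsor investigates whether the type and severity of the event were anticipated. If an adverse event (AE) is found to pose unreasonable risk, the sponsor must act on terminating the study, within 15 working days of notice. Section 11.6 lets the sponsor suspend enrollment over protocol deviations. Section 14.9 covers who is told when the study is suspended or stopped.

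**The concern.** The rule in 5.2 moves or keeps the setting from subject to subject, but the SAE procedures in section 7 work at the level of the whole study and on a scale of weeks. Nothing joins the two. Section 7.3 lists anticipated events that a discomfort rating does not measure, such as perforation, infection and urethral stricture. If one of these occurred as a related SAE in a subject who found the treatment bearable, 5.2 read literally would carry the setting forward. A finding under 7.6 that the event was anticipated would not by itself change it.

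The same gap affects increases: no interval is set between treating a subject and raising the setting for the next. At stake is avoidable exposure of later subjects to a setting whose acute safety has not been looked at.

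**Working it through.** The plan states no error rate, power, target event rate or stopping boundary, so it has no figure to reproduce. The check sets the relevant text side by side and then sizes what can be sized.

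1. **What the rule in 5.2 uses.** It uses toleration. The nearby text names pain, swelling and discomfort during and after the procedure. AEs and catheterization are collected, but no sentence makes them a condition for reusing or raising a setting.

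2. **What could pause treatment at a setting.**
 - 7.6, reporting: up to 10 working days; no pause meanwhile.
 - 7.6, sponsor investigation: the question is whether the event was anticipated, not whether the setting should be reused.
 - 7.6, termination: whole study, up to 15 working days from notice; not by setting.
 - Table 13-1, death: 48-hour report; no pause.
 - 11.6: suspension of enrollment, triggered by deviations.
 - 14.9: notification only.

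 None requires a hold at a setting while a related SAE is reviewed.

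3. **What fixes an interval before an increase.** Nothing. The 24-hour stay in 5.3.2 is observation of the treated subject; no text makes it a gap before the next subject. Table 6-1 has visits at days 1-2 and days 4-7, with none between.

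4. **Why the look-back needs all catheterizations.** Section 7.1 says: "The reason for catheterization will not be considered an AE if catheterization occurs and ends within 72 hours after the procedure". (A recurrence does count.) Section 7.2 similarly leaves out listed symptoms of 72 hours or less unless they lead to intervention or to further or prolonged hospital care. A review of AEs alone would therefore miss short catheterizations, so Endpoint 2 must be read alongside them.

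5. **Subjects under the rule.** Up to 15 - 1 = 14 subjects are treated after the first. This counts who falls under the rule and is not an estimate of harm.

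6. **Cost of waiting to 72 hours, counted from the procedure.** Each increase waits up to 72 h = 3 days. The plan gives no step size, so 25 W is assumed:
 - Increases: (250 - 175)/25 = 3. Total wait: 3 x 3 = 9 days.
 - Lower end, one increase: 1 x 3 = 3 days.
 - Upper end, a new setting for every subject after the first: 14 x 3 = 42 days.
 - If the site would wait out the 24-hour stay in any case, the added time is 72 - 24 = 48 h = 2 days per increase: 3 x 2 = 6 days, range 1 x 2 = 2 to 14 x 2 = 28 days.

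 The 72-hour count from the procedure is the one to use, because the plan does not require the shorter baseline.

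**The case against.** The best defence is practical. This is one site, and the Principal Investigator would normally learn of an SAE first and may simply pause. A clinician may naturally read *tolerate* to include SAEs; the lowest severity grade in 7.8 is itself worded in terms of toleration. Settings move only slightly, inside a range fixed by bench, animal and extirpated-tissue work. Section 1 reports more than 60 canine studies and 4 + 9 = 13 subjects treated with an earlier version of the device, and up to 20 acute subjects come first in Phase 1. The instructions for use and the monitoring plan are cited but not included, so a hold written there cannot be ruled out.

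All of this lowers the stakes, and none of it supplies the hold. Phase 1 has no follow-up, so it says little about events after the procedure, and the power range was set for lesion size.

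A reader might infer that the plan ignores safety when choosing settings, or permits open-ended escalation. The documents do not support that: adverse responses are collected for every setting, catheterization is an optimization endpoint in its own right whatever its AE status, the range is bounded, and the sponsor has a duty to act on unreasonable risk. A reader might also treat the lack of criteria for *tolerate*, or of a by-setting table in 14.2, as the main defect. These are points of wording. The changes proposed here leave toleration to clinical judgement, and 14.2 already permits by-setting summaries where appropriate.

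**Conclusion.** The point holds as a cheap improvement, with medium confidence. The written rule lets a setting be reused after a related SAE before review, and lets it be raised with no minimum observation. That is a statement about what the protocol requires, not a prediction of what the site would do.

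The size of the harm is unknown, because event rates, step size and accrual pace are not given. The cost of closing the gap is small beside the five-year follow-up. The cost figure assumes 25 W steps and at most one change of setting per subject. The conclusion rests on the protocol text alone and would weaken if the instructions for use or the monitoring plan already require a hold.

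**What to change.** Amend 5.2, for Phase 2 only.

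1. **Hold after a related SAE.** Any SAE (7.4) rated definite, probable or possible (7.7) stops treatment at that power setting or any higher one. The hold runs from when the Principal Investigator learns of the event until the Principal Investigator and sponsor document a decision to resume or revert. Order settings by nominal power with its paired water flow; if a subject received more than one setting, the lowest one used counts. Lower settings may continue; if none is available, treatment waits for the decision.

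2. **Look-back before an increase.** No increase until the most recent subject at the current setting has passed 72 hours and the Principal Investigator and sponsor have reviewed discomfort, related AEs and all catheterizations at that setting, including those ending within 72 hours.

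Section 7.6 can stay as it is, and no committee is needed.

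The cost is the wait worked out above, a 72-hour phone call where the clinic record does not cover it, and SAE pauses whose length cannot be stated in advance. Some pauses will follow SAEs later judged unrelated, because *definite* in 7.7 rests on timing alone. One amendment is needed under 11.4, with written agreement between sponsor and investigator and ethics committee approval. The data are already collected.
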